This will be an open label, single site, pilot, clinical research study. Up to 40 active duty military personnel, or recent Veterans, age 18 or older, who have been diagnosed with PTSD, have received treatment for, are referred by military medical personnel for, or have active symptoms of militaryrelated traumatic stress, with or without mild TBI, will be recruited to receive up to 24 HIRREM sessions over 2 weeks. For those who self-refer, and do not have a prior diagnosis or treatment for PTSD, active symptoms will be identified by a screening PCL-M score of 50 or greater. Recruitment of 40 participants will allow us to achieve the goal of 36 participants to complete the intervention, allowing for the possibility of dropouts. The primary outcome will be differential change in the PCL-M from baseline to completion of HIRREM sessions. Secondary measures include the Insomnia Severity Index (ISI), the Center for Epidemiological Studies Depression Scale (CES-D), an anxiety measure (GAD-7), a quality of life measure (EQ-5D), an autonomic symptom measure (Compass 31), and a daily sleep diary, as well as physiological measures including heart rate (HR), and blood pressure (BP), with calculation of heart rate variability measures (HRV), and baroreflex sensitivity (BRS). Functional measures will include reaction time (drop-stick paradigm), and grip strength (hydraulic dynamometer), and analysis of brain patterns. If there is a history of TBI, a Rivermead Post-Concussion Symptoms Questionnaire (RPQ) will be added. There will be pre- and post-intervention data collection for all measures (baseline, V1, and at completion of HIRREM sessions, V2). Self-report measures will also be repeated by phone at 1, 3, and 6 months after completion of sessions (V3, V4, and V5 respectively). The online sleep diary will be maintained from V1 until V3. A brainwave assessment will be obtained at V1.

Participants/Subjects

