All baseline measures, along with a brainwave assessment, will be obtained during a Monday morning enrollment visit (V1), and a daily sleep diary will be started. All V1 measures will require 3-4 hours to complete. The online sleep diary will be maintained until the one month post-HIRREM follow-up phone call. The HIRREM sessions will begin in the afternoon following the V1 data collection, and can be done with 2 sessions during a half day period. The sessions will typically be about 1.5-2 hours in length. Each session will typically include between 4 to 10 protocols, lasting from 6 to 40 minutes each. Some protocols will be administered while the participant is sitting upright, with eyes open, while others will be with eyes closed, in a reclining position. Participants will receive up to 24 HIRREM sessions over a two week period, although most will receive 20, during 10 half days, over a two week period.

A post-HIRREM data collection (V2) will occur after the final HIRREM sessions, typically on Friday afternoon, of the second week. All measures obtained at the V1 data collection visit, except for the brainwave assessment, will be repeated. The V2 data collection will take about 2.5 to 3.5 hours to complete. Additional follow-up data collection, for self-reported symptom inventories, will be done by telephone at 1 month (V3), 3 months (V4), and 6 months (V5) following completion of HIRREM sessions. Thus, all participants will have 5 data collections (V1-5), and will receive HIRREM intervention during a two week period between V1 and V2. Total time of study participation will thus be about 9.5 months.

Summary of Projected Typical Study Flow:

- Sunday: Arrival in Winston-Salem
- Monday (week 1): 0800 Enrollment/baseline data collection (V1), followed by HIRREM sessions (1-2)
- Tuesday-Friday (week 1): Two HIRREM sessions per day (sessions 3-10)
- Sat-Sun: R & R (potential for up to 4 additional sessions if needed)
- Monday-Thursday (week 2): Two HIRREM sessions per day (sessions 11-18)
- Friday (week 2): Last 2 HIRREM sessions (sessions 19-20), and post-HIRREM data collection (V2)
- Departure: Late Friday afternoon, or Saturday
- Post-HIRREM telephone data collections at one month (V3), three months (V4), and six months (V5) after completion of HIRREM sessions

A) Enrollment Visit

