Informed consent obtained, a brief medical history obtained (Appendix), and collection of baseline measures, to include a HIRREM assessment, evaluating brain frequencies and amplitudes, as well as an MRI scan, and blood/saliva samples, are obtained at the enrollment visit (V1). The Clinical Research Unit (CRU) will assist with the blood collection for this study. This will occur prior to the start of HIRREM sessions, and will require about a total of 3-4 hours. When possible the completed medical history form may be requested and received prior to the enrollment visit. Instructions will be provided regarding completion of a daily sleep diary. This will be collected using an online survey (REDCap), and will be continued through the V3 follow-up phone call, one month after completion of the intervention.

B) HIRREM Sessions

Participants may receive two HIRREM sessions in a half day period for an anticipated total of 20 HIRREM sessions per participant, with 10 half days spent during the two weeks of HIRREM. Some participants may receive up to 24 HIRREM sessions, over the course of 12 half days, if sessions are recommended to be done over the intervening Saturday and Sunday. Sessions last about 1.5-2 hours, and two can be done in a half day, with a short break (20-60 minutes) between sessions.

C) Post-Intervention Data Collection Visit

On the afternoon following the final HIRREM session, a post-HIRREM data collection visit will occur (V2). This will typically be on Friday afternoon of the second week of participation. All measures will be repeated, but no brainwave assessment will be done. This visit will take 2.5-3.5 hours.

D) Late Follow-Up Data Collection

One month after completion of V2, participants will be contacted by telephone to collect repeated symptom inventories (V3). The daily sleep diary will be discontinued after this call. This call should take about 30 minutes.

Three months after completion of V2, participants will be contacted on the phone to collect repeated symptom inventories (V4). This call should take about 30 minutes.

Six months after completion of V2, participants will be contacted on the phone to collect final repeated symptom inventories (V5). This call should take about 30 minutes, and will complete participation in the study.

3) High-resolution, relational, resonance-based, electroencephalic mirroring (HIRREM)

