The proprietors of HIRREM have repeatedly observed that EEG asymmetries in the temporal lobes (specifically at T3 and T4 in the 10-20 International System for EEG correspond to autonomic dysfunction. When T4 signals are dominant to T3 signals a sympathetic state is favored which is manifested as symptoms of anxiety, cardiovascular over-drive, and hyperarousal. When T3 signals are excessively dominant to T4 signals a parasympathetic state is favored which is manifested as symptoms of emotional numbness, cardiovascular underactivity, GI dysfunction, and under-arousal. Lateralization of autonomic activity is not a novel finding, it is in accord with a number of previously published studies which support a hypothesis of autonomic lateralization⁴⁶.

EEG balance at T3 and T4 suggests autonomic balance and benefit, and our preliminary results suggest that utilization of HIRREM at T3 and T4 has demonstrated success in ameliorating symptoms associated with autonomic disruption^{31,47} Preliminary data also demonstrate correlation between a T3/T4 temporal asymmetry score and objective physiological changes reflective of autonomic signaling to the heart at the baseline assessment (AAN T3/T4 2013

poster). Reduction in the sum of high frequency amplitudes at T3/T4 (reduced hyperarousal), has also been observed in subjects with hot flashes⁴⁸. Comparison of such activity at T3 and T4 over time will provide objective physiological outcome data regarding the effect of HIRREM on autonomic balance and function.

5) Statistical Analysis

Data will be analyzed using the most recent versions of SAS (SAS Institute, Inc., Cary, NC) or the R Statistical Computing Environment. Histograms and descriptive statistics will be examined to evaluate the distribution of study outcomes. Because this proposal is designed to estimate effect sizes for future randomized trials, analyses will primarily consist of providing point estimates of effect size for each outcome along with corresponding 95% Cls. Given that outcomes will be collected at multiple follow-up time points (V2, V3, and V4), effect estimates will be based on generalized linear models, which can accommodate within-subject correlations due to repeated assessment over time. Critically, estimates produced from this pilot study will need to be used cautiously for planning future research, as it is well known that estimates from small sample sizes tend to be upwardly biased (overestimated effect sizes, underestimated variability⁵³.

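### Does a morning baseline and an afternoon post-treatment visit for the physiological and functional measures call for a change to the plan?

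*Combined protocol and SAP*

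**What the plan says.** All references are to the combined protocol and SAP.

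- **Baseline.** The section on number of sessions and length of study says "All baseline measures, along with a brainwave assessment, will be obtained during a Monday morning enrollment visit (V1". The typical study flow gives the clock time: "Monday (week 1): 0800 Enrollment/baseline data collection (V1), followed by HIRREM sessions (1-2". V1 takes 3-4 hours, and the first sessions come that afternoon.
- **Post-intervention.** The same flow lists "Friday (week 2): Last 2 HIRREM sessions (sessions 19-20), and post-HIRREM data collection (V2". The section on the post-intervention visit agrees: "On the afternoon following the final HIRREM session, a post-HIRREM data collection visit will occur (V2". V2 takes 2.5-3.5 hours.
- **What is measured when.** The Overview says "There will be pre- and post-intervention data collection for all measures (baseline, V1, and at completion of HIRREM sessions, V2". For later contacts it says only "Self-report measures will also be repeated by phone at 1, 3, and 6 months after completion of sessions". The supine recording (heart rate, blood pressure, heart rate variability, baroreflex sensitivity), reaction time and grip therefore have one post-baseline value each. The self-report inventories have four.
- **Analysis.** Under Statistical Analysis, "analyses will primarily consist of providing point estimates of effect size for each outcome", with 95% intervals. The estimates are to be "used cautiously for planning future research, as it is well known that estimates from small sample sizes tend to be upwardly biased". Measurement timing is not mentioned there.

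**The concern.** On the typical schedule every participant is measured in the morning before any session at V1, and in the afternoon after two sessions at V2. An effect of the sessions themselves, including a short-lived one, belongs to what the plan sets out to estimate, namely change at completion of sessions. A time-of-day effect does not, yet it would be included in the same number.

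The Secondary Objectives expect autonomic change, faster reactions and stronger grip, and the Number of Subjects section says the estimates are meant for planning randomized studies. A planner who read only the Statistical Analysis section would be warned about small samples but not about timing, and the confidence interval would not reveal the problem. If a material diurnal shift existed, a later trial could be sized on a change that is partly due to the clock.

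**Working it through.** **1. The plan's own precision figure.** Inputs are the SD of 20.0 and n = 10 from the summary's sample size paragraph. Half-width = 1.96 × 20.0 / √10 = 12.4 points, which reproduces. It applies to the PCL-M; the documents give no SD for the six measures considered here, so SD units are used below.

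**2. Can timing be separated from treatment?** Code each participant's two rows as (intercept, post-HIRREM, afternoon, sessions that day). V1 is (1, 0, 0, 0) and V2 is (1, 1, 1, 1). There are only two distinct rows, so the matrix has 4 columns and rank 2 at any sample size. The repeated-measures model does not help, because these outcomes have no second post-baseline value. The aliasing is therefore real.

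It is not specific to clock time. Add a column for day of week, for travel to the site or for practice with the test. Each is again 0 at V1 and 1 at V2, and the rank stays at 2.

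**3. How large is the clock gap?** V1 runs from 0800 to 1100-1200 (0800 plus 3-4 h). Two sessions of 1.5-2 h with a 20-60 minute break take from 2 × 1.5 h + 20 min = 3 h 20 min to 2 × 2 h + 60 min = 5 h. The Friday start time is not stated. Assuming 0800, sessions end between 1120 and 1300. V2 is an afternoon visit, so it starts between about 1200 and 1300 and ends by 1300 + 3.5 h = 1630.

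- Smallest gap: tested last at V1 (1200) and first at V2 (1200), 0 h.
- Largest gap: tested first at V1 (0800) and last at V2 (1630), 8.5 h.

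Test order within visits is not given, so the documents do not place any measure within this range. A later Friday start would move V2 later.

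**4. What would an assumed shift do?** With 36 completers the 95% half-width is t(35)/√36 = 2.030/6 = 0.34 SD of change; with 40 it is 2.023/6.325 = 0.32 SD. This is sampling error only and says nothing about the size of a timing effect.

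As an illustration, suppose there were no treatment effect and a pure timing shift of d SD. Using the normal approximation, the chance that the interval excludes zero is Φ(−1.96 + 6d) + Φ(−1.96 − 6d).

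| Assumed d | Chance |
|---|---|
| 0.2 | 22% |
| 0.3 | 44% |
| 0.5 | 85% |

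These values of d are assumptions. Nothing in the documents supports any of them, or a direction.

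**5. Does it carry into the next trial?** Let h be the treatment effect and c everything else that changes between the visits, timing included. A single arm estimates h + c. A randomized trial with both arms on one schedule estimates (h + c) − c = h. So c affects how this pilot's changes are read as planning values. It does not bias the between-arm comparison they lead to.

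**The case for a change.** The strongest case for acting is that the remedy costs almost nothing. The plan itself tells planners to be cautious and then gives only one reason. The measurement sections fix posture, recording length and number of trials in detail, but set no clock time and no interval since the last session. Morning-to-afternoon timing is a particular feature of this schedule, and calling the study an open-label pilot does not by itself announce it. One sentence and a line of measurement times would cover everyone, including participants already measured.

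What stands is that the Statistical Analysis section does not mention timing, and that these six outcomes have no later value to check against. What does not follow is a defect in the plan. The hours and days are printed in the visit schedule, and nothing in the analysis section claims that these changes isolate a causal effect. The added sentence would repeat the schedule without removing or measuring any difference. Singling out time of day from the many factors that move with the visit might also suggest that the rest had been dealt with.

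The breadth is smaller than six outcomes suggests. Four of them come from one standardized supine recording of at least 10 minutes, so only three procedures are involved. Nor are these same-day changes. They run from Monday of week 1 to Friday of week 2, 7 + 4 = 11 days; only V2 and the last two sessions share a day.

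**Conclusion.** No change to the plan is needed. On the typical schedule, time of day and the post-treatment visit are fully aliased for the supine recording, reaction time and grip. The size of any resulting distortion is unknown: the documents give no effect, no direction, and a clock gap of 0 to 8.5 hours under an assumed 0800 Friday start. This is one instance of the general limit of a single-arm before-and-after pilot, which the protocol openly accepts. It is a fair trade-off for fitting baseline, about 20 sessions and the final visit into a two-week stay.

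No estimate, interval, procedure or stated figure would be altered by a caveat. Authors may still choose to report actual measurement times, and to describe these results as two-week changes from a morning visit to an afternoon visit. That is an option for the report.

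The conclusion assumes that most participants follow the typical flow, that these secondary changes remain descriptive, and that later trials use a concurrent control on a common schedule. It would not hold if the six changes were presented as evidence of efficacy in their own right, or used directly as between-arm effects.

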A strong negative correlation (-0.823, p < 0.0001) existed between asymmetry at baseline and change from baseline based on the penultimate minute of the final HIRREM session, indicating a reduction in asymmetry over the course of sessions. The sums of T3 and T4 high frequency amplitudes decreased from baseline to the final session (p < 0.0001). SDNN increased significantly from baseline to the

ultimate minute (p = 0.0006). Changes in heart rate and other autonomic metrics were not statistically significant.

In this case series, HIRREM technology was applicable as a way to 1) assess autonomic balance, 2) facilitate reductions in hemispheric electroencephalic asymmetry, 3) decrease total amplitudes at T3/T4, and 4) facilitate improved HRV (SDNN)¹⁸. The strength of the observed correlations and effect sizes may have been attenuated by the heterogeneity of the population. To our knowledge, these data are the first showing that cerebral hemispheric lateralization in autonomic management can be easily leveraged for clinical assessment and intervention (presented as a poster at the annual meeting of the American Neurological Association, October, 2013, New Orleans, LA).

Study Objectives:

Primary Objective:

The primary objective of this clinical research study is to estimate the effectiveness of HIRREM plus usual care in reducing symptoms of military-related traumatic stress as measured by the PCL-M, among military personnel and veterans who have been diagnosed with PTSD, have been treated for, are referred by military medical personnel for, or have active symptoms of military-related traumatic stress, with or without TBI.

Secondary Objectives:

Secondary objectives include evaluation of the effect of HIRREM on:

- Autonomic nervous system functions, as manifested by blood pressure, heart rate, and HRV. We expect to see changes in autonomic activity and an improvement of sympatho-vagal balance, which would be reflected as changes in heart rate, and an increase of HRV parameters such as the standard deviation of normal R-R intervals (SDNN).
- Psychological symptoms such as depression, assessed by the CES-D symptom inventory. We expect to see improvement in this symptom score.
- Anxiety, as assessed by the GAD-7 symptom inventory. We expect to see reduced anxiety scores.
- Quality of life as evaluated using the EQ-5D measure. We hope to see improved overall quality of life scores.

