Continuous BP and HR are acquired from noninvasive finger arterial pressure measurements and ECG for a minimum of 10 minutes in subjects lying down quietly, supine. Systolic BP and beat to beat, RR, intervals (RRI) files generated via the data acquisition system (BIOPAC acquisition system and software, Santa Barbara, CA) at 1000 Hz are analyzed using Nevrokard BRS software (Nevrokard BRS, Medistar, Ljubljana, Slovenia) for measures of BRS, HRV and BPV as follows: Frequency Method. Power spectral densities of SBP and RRI oscillations are computed by 512 points Fast Fourier Transform (FFT) and integrated over specified frequency ranges (LF: 0.04-0.15 Hz; HF: 0.15-0.4 Hz). A Hanning window is applied and the squared-coherence modulus is computed if coherence is > 0.5 as reported. The square-root of the ratio of RRI's and SBP powers is computed to calculate LF, HF alpha indices, which reflect BRS. Power of RRI spectra in LF, HF range (LFRRI and HFRRI) are calculated in normalized units and the ratio of LFRRI/HFRRI is used as a measure of sympatho-vagal balance. Power of SBP spectra calculated as LFSAP is used as a measure of BPV. Sequence Method - BRS calculated by this method is based on quantification of sequences of at least three beats (n) in which SBP consecutively increases (UP sequence) or decreases (DOWN sequence), which are accompanied by changes in the same direction of the RRI of subsequent beats (n+1). The software scans the RRI and SBP records, identifies sequences, and calculates linear correlation between RRI and SBP for each sequence. If the correlation coefficient exceeds a pre-set critical value (0.85), the regression coefficient (slope) is calculated and accepted. The mean of all individual regression coefficients (slopes), a measure of sequence BRS, is then calculated for Sequence UP, DOWN and TOTAL. Time-Domain Analysis - Three time-domain parameters are used for hemodynamic variability. HRV is determined by computing the standard deviation of beat-to-beat interval (SDNN) and the root mean square of successive beat-to-beat differences in R-R interval duration (rMSSD).

a) HRV Data Processing and Interpretation

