Heart rate is measured as beat-to-beat intervals (RRI) recorded by pulse-wave recording, and will be analyzed using custom software developed by Biopac. Data can be loaded and viewed, and a subset of the data can be selected to avoid artifacts during device placement or removal. Outlier identification is performed by determining all inter-beat intervals which demonstrate a 30% difference from the mean of the previous four samples. Such outliers are removed from the data set. HRV statistics that are generated include mean, variance, SDNN, RMSSD, pNN50, VLF, LF, HF, TP, LF/HF, sample

Version 1.0 10/06/2017

rpq

asymmetry, sample entropy, and coherence. All of the algorithms for computation of these parameters are derived from information or source code from the Physionet archive. Data are saved to Excel spreadsheets for further statistical analysis by study team members.

b) Blood Pressure (BP)

Blood pressure (BP) measurements will be taken with a finger cuff on two fingers of the left hand while lying down on an examination table.

Functional Measures:

Reaction Time

Reaction time testing will be measured by a drop-stick, clinical reaction time apparatus. It is constructed from a meter stick covered in the friction tape with gradations. The modified meter stick is fixed to a weighted rubber cylinder. The apparatus is placed between the thumb and index finger of the subject and released at a random time during a countdown. The subject catches the apparatus and the distance fallen is converted to reaction. Following two practice trials, subjects perform eight trials, and a mean distance value is used for analysis. This simple clinical measure has been evaluated by Eckner et al, and demonstrated utility in testing comparable to computerized testing methods²⁸. ⁴⁴

Grip Strength

Grip strength will be evaluated using a hydraulic hand dynamometer (Baseline Hydraulic Hand Dynamometer). The greatest force generated during three trials will be used for analysis²⁹.⁴⁵

Brain Pattern Analysis

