6) Participant Compensation

Participants in this research project will not receive any monetary compensation.

Human Subjects Protection:

1) Consent and Assent

Written informed consent, or assent and parental permission will be obtained by the research staff from each competent subject.

2) Confidentiality and Privacy

Confidentiality will be protected by collecting only information needed to assess study outcomes, minimizing to the fullest extent possible the collection of any information that could directly identify subjects, and maintaining all study information in a secure manner. To help ensure subject privacy and confidentiality, only a unique study identifier will appear on the data collection form. Any collected patient identifying information corresponding to the unique study identifier will be maintained on a separate master log. The master log will be kept secure, with access limited to designated study personnel. Following data collection subject identifying information will be destroyed at the earliest opportunity, consistent with data validation and study design, producing an anonymous analytical data set. Data access will be limited to study staff. Data and records will be kept locked and secured, with any computer data password protected. No reference to any individual participant will appear in reports, presentations, or publications that may arise from the study.

Brain State Technologies, LLC (BST) will assist with brain pattern analysis. To accomplish this, BST will be provided with the first 8 characters from the randomly generated, 36 character identifier that the HIRREM software generates for each participant's brain frequency and amplitude data, along with the participant's age and gender, which are believed important for understanding brain patterns. No other participant-specific information is provided.

3) Data and Safety Monitoring

The principal investigator will be responsible for the overall monitoring of the data and safety of study participants. The principal investigator will be assisted by other members of the study staff. Results will also be regularly reviewed with representatives of OSD, the funding agency.

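### HRV segments may be chosen after viewing the record with no fixed window and no masking to visit, and no masking to session order is described for the brain-pattern analysis, in which the technology's creator assists

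*Combined protocol and SAP*

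**What the plan says.** All references are to the combined protocol and SAP.

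- **Design.** The Overview under Research Design and Method states: "This will be an open label, single site, pilot, clinical research study". No masked processing is described for any outcome.
- **HRV recording.** Under Physiological measures, blood pressure and heart rate are recorded "for a minimum of 10 minutes in subjects lying down quietly, supine". That is a minimum, not an analysed length.
- **HRV processing.** Under HRV Data Processing and Interpretation, the record can be loaded and viewed, and "a subset of the data can be selected to avoid artifacts during device placement or removal". A rule-based step follows: "Outlier identification is performed by determining all inter-beat intervals which demonstrate a 30% difference from the mean of the previous four samples", and the flagged intervals are dropped. Then: "Data are saved to Excel spreadsheets for further statistical analysis by study team members".
- **Expected direction.** Under Secondary Objectives: "We expect to see changes in autonomic activity and an improvement of sympatho-vagal balance", with a rise in measures such as SDNN. The same list expects better balance and less hyperarousal in the brain pattern.
- **Brain-pattern data.** Secondary Objectives takes these from the baseline assessment and from later sessions, without naming a session, minute or epoch. The brainwave assessment is not repeated at V2.
- **Who analyses it.** Under Confidentiality and Privacy, the company that created HIRREM "will assist with brain pattern analysis". It receives a shortened software identifier, age and gender, and nothing else specific to the participant.
- **Weight placed on it.** Under Brain Pattern Analysis: "Comparison of such activity at T3 and T4 over time will provide objective physiological outcome data".

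**The concern.** Participants in this study cannot be blinded, and self-report cannot be masked. Stored recordings can. When the person choosing a stretch of HRV record may know whether it is V1 or V2, and the hoped-for direction is written down, small defensible choices can lean the same way across participants. The same applies to the choice of EEG epoch, with the added point that one of the parties assisting created the technology under study.

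The plan's stated product is an effect size with a 95% interval for each outcome, to plan randomized trials. A lean in processing shifts the point estimate and is not reflected in the interval. The Statistical Analysis section warns of upward bias from small samples but says nothing about bias from unmasked processing.

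**Working it through.** **1. Is there a design figure to reproduce?** Not for these outcomes. The only precision figure is for PCL-M: 1.96 × 20.0 / √10 = 12.40, which matches the stated ±12.4. It does not bear on HRV or EEG. The check is therefore mainly a comparison of passages.

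**2. How much is left open for HRV?**

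| Element | Stated? |
|---|---|
| Reason for selecting a subset | Yes: artifacts when the device is put on or taken off |
| Recording length | Minimum of 10 minutes only |
| Analysed length | No |
| Start of the analysed window | No |
| Who selects | No |
| Masking of the selector to visit | No |
| Outlier removal | Yes, fixed 30% rule |

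The 30% rule is automatic, but nothing in the text makes it fix which stretch is analysed. Two processing routes also appear: ECG and finger pressure analysed with Nevrokard under Physiological measures, and pulse-wave intervals analysed with custom Biopac software under HRV Data Processing. The text does not say which supplies the HRV outcome.

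**3. How much is left open for the brain pattern?** Most participants receive 20 sessions and some up to 24, each with 4 to 10 protocols. That is between 20 × 4 = 80 and 24 × 10 = 240 protocols per participant. How many are at T3/T4 is not stated. With no V2 assessment, the post-intervention value must come from session recordings, and none is designated. The pilot work shows the choice is real: in the section on brain pattern and autonomic function, the asymmetry change uses the penultimate minute of the final session, while the amplitude sum is reported only to the final session.

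**4. What does the company see?** One identifier per participant, constant across that participant's data. Session order is neither shown nor hidden by anything in the text.

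**5. Illustration of scale for SDNN.** The pilot change, from the TBI case series, is 65.2 − 51.8 = 13.4 ms. Assume (not in the documents) *k* equally acceptable segments per record and a within-record SD of segment SDNN of 3 to 10 ms. If the most favourable segment were always taken at V2 only, the expected spurious gain is E[max of *k* standard normals] × SD:

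- *k* = 2: E = 1/√π = 0.564, giving 0.564 × 3 = 1.7 ms to 0.564 × 10 = 5.6 ms.
- *k* = 3: E = 3/(2√π) = 0.846, giving 0.846 × 3 = 2.5 ms to 0.846 × 10 = 8.5 ms.

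Against 13.4 ms this runs from 1.7/13.4 = 13% to 8.5/13.4 = 63%. If instead only a quarter of choices leaned, at both visits, with *k* = 2 and SD 3 to 8 ms, the shift is 0.25 × 2 × 0.564 × SD = 0.8 to 2.3 ms. With a fixed window applied without knowledge of visit, this component is zero in expectation. No comparable illustration is offered for the EEG, because the documents give nothing to scale it on.

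**The case against.** The strongest reply is that the HRV text describes trimming, not free choice: a subset may be taken, for one named technical reason, and a fixed outlier rule follows. The company receives almost nothing about each participant. These are secondary outcomes in an open-label pilot, and in a single-arm pre/post comparison even perfectly masked HRV would not separate a treatment effect from time or regression to the mean.

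Much of this stands, and it rules out stronger readings that a reader might be tempted to infer:

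- **That HRV data are in fact hand-picked.** The text permits selection; it does not say selection is routine.
- **That analysts see visit or session order.** Nothing says so. The documents are silent, and the criticism is of that silence.
- **That HRV is also labelled objective.** For a planned outcome, that word is attached to the T3/T4 comparison.
- **That these are the only outcomes able to support PCL-M.** Reaction time and grip strength are also measured, and baroreflex sensitivity is computed by software thresholds.
- **That any lean could never be found later.** If raw files are kept, they can be re-run with a fixed window.

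What does not stand is the inference that nothing needs changing. Trimming for artifacts still leaves the start and length open in a record with no stated maximum. Limiting participant information protects privacy and does not address session order.

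**Conclusion.** The point holds in a limited form. The plan leaves HRV segment choice without a fixed window or masking to visit. It describes no masking to session order for a brain-pattern outcome that it calls objective and that the technology's creator helps analyse. The resulting risk of bias is avoidable.

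It is confined to secondary outcomes; PCL-M is untouched. The size cannot be computed from the documents. The range of 1.7 to 8.5 ms for SDNN rests on an assumed within-record SD, an assumed number of interchangeable segments, and favourable selection every time at V2. It shows that the issue could matter on the scale of the pilot change, and says nothing about how anyone has behaved or will behave.

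**What to change.** **HRV Data Processing and Interpretation.**
1. Rename all stored blood pressure and ECG files, V1 and V2, including those already collected, with random codes held by a team member who does not process files.
2. Pre-specify one analysis window: a fixed length and a fixed start after device placement, together fitting within the 10-minute minimum. State which of the two software routes supplies the HRV outcome.
3. Apply the window and lock any artifact exclusions on the coded files. Only then link files to visit.

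**Secondary Objectives (brain pattern) and Confidentiality and Privacy.**
1. Fix in advance which session and which minute supply the post-intervention T3/T4 epoch.
2. Send epochs to the company under a separate code for each epoch, without date or session number, and link order after results are returned.
3. Describe the EEG result as only partly masked: the baseline assessment and the session recordings differ in kind, so order may be recognisable.

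**Cost.** A renaming script, a short written procedure and a small delay, with no extra visit or participant. One team member has to stay out of file processing. Existing files need reprocessing so that two methods are not mixed: the Addendum describes 18 participants with physiological outcomes before the later expansion, or 18 × 2 = 36 recordings, and full enrolment would give at most 40 × 2 = 80. Selection of protocols during sessions is unaffected.
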